3.5. RANDOMIZATION AND BLINDING

The Phase 2a study will be partially blinded. The patient and investigator will be blinded as to whether TK-112690 or placebo is administered. The CRO, sponsor, and site pharmacist will know whether the patient was administered active drug or placebo.

A list providing randomization, active drug and placebo, for each of the 22 subjects will be prepared (List A). Another list will provide randomization for 8 additional subjects if additional subjects are enrolled (List B). Both lists will be kept by the CRO.

A designated person or Pharmacist will prepare the TK-112690 treatments by adding either active drug or placebo into 250 ml 0.9% sodium chloride iv bottle (**Appendix 3**). Whether active drug or placebo is added will reflect the subject number and the randomization suggestion made in the Randomization List for that subject number. The CRO will provide the designated person or pharmacist with vials re-labelled to maintain the partial blind. The randomization will be done by the CRO or a third-party vendor.

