5.5. BLIND\CODE BREAK

Phase 2a is a partially blinded study. The patient and investigator will be blinded as to whether TK-112690 or placebo is administered, and the CRO, Sponsor, and site pharmacist (unblinded) will know whether TK-112690 or placebo, was administered. The Pharmacist will be receiving all the vials from CRO, on randomization to a particular group the unblinded pharmacist will take the IP\Placebo and mask it with a white sticker so that the blind is maintained at all times. At the request of the investigator, the code can be broken. A Subject's treatment assignment will not be broken until the end of the study, unless medical treatment of the subject depends on knowing the study treatment the subject received. In the event that the blind needs to be broken because of a medical emergency, the investigator may unblind an individual subject's treatment allocation. As soon as possible, the investigator should first contact the medical monitor to discuss the medical emergency and the reason for revealing the actual treatment received by that subject. It should be documented in the case record form. For unblinding, investigator may also ask the medical monitor, who will in turn ask the unblinded statistician to provide the code to the investigator for the particular subject. The date on which the code was broken, together with the identity of the person responsible, must also be documented. When the investigator unblinds a patient treatment for emergency reasons, he/she must note the date, time, and reason for doing it and record this information in the source notes.

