6.7. CLINICAL LABORATORY TESTS

6.7.1. Laboratory Parameters

Nitrite pH

Besides the Central Laboratory Tests, an in-house (at site) CBC, Kidney function test, Liver function test will be performed to qualify the subject for dosing with MTX, .Coagulation: (prothrombin time, PT, and activated partial thromboplastin time, PTT,tests will be performed at the Local laboratory associated with the clinical site as per schedule of events.

Subjects will be in a seated or supine position during blood collection. Clinical laboratory tests to be performed are included in **Table 10**. **Table 10**. **Central Laboratory Tests**

Hematology:SerumHematocrit (Hct)Hemoglobin (Hb)Mean corpuscular hemoglobin concentration (MCHC)Mean corpuscular volume (MCV)Platelet countRed blood cell (RBC) countWhite blood cell (WBC) count with differential	Blood urea nitrogen (BUN) C-reactive protein Calcium (Ca) Chloride (Cl) Creatinine Creatinine kinase Direct bilirubin Total bilirubin Total cholesterol (non-fasting) Total protein Triglycerides (non-fasting) Uric acid Gamma-glutamyltransferase (GGT) Globulin Glucose (Random)
Urinalysis :(will be performed by dipstick) Appearance Color Glucose Protein Occult blood	

Urine human chorionic gonadotropin: Females of childbearing potential only

Coagulation:

- Prothrombin time (PT)
- Activated partial thromboplastin time (PTT)

The laboratory measurements of clinical chemistry, hematology and urinalysis will be performed during screening (defined as baseline), on Day 0 and at 24 and 48 hours post each initial infusion of TK-112690 or Placeboas well as on Day 1 of Week6.

All laboratory measurements will be performed at a central laboratory. The laboratory will provide the PI and Tosk with test results including units, relevant reference ranges and updates as necessary. Laboratory measurements can also be performed at local sites for medical or informational reasons However; these measurements will not be considered part of the study record.

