6.7.4. Blood Samples

A blood sample for CBC, Kidney function test, Liver Function test determination will be obtained 24 hours or so before each MTX dose to assure the patient is suitable for treatment with this chemotherapeutic. The sample will be processed at the local laboratory associated with the clinical site, and the data provided to the PI, the CRO and Tosk.

6.7.5 Summary of Blood Samples to be obtained.

A summary of the blood samples to be obtained in the study is provided in **Table 11**.

Table 11. Nature and total volume of blood samples

Purpose	Size (mL)	Time	Total Volume (mL) / Patient
CBC, Kidney function test, Liver Function test	7	Pre-dose Weeks 1-4	28

Laboratory Test	14	Screening Day 0 Weeks 1-4 (24 and 48 hours) Week 6	154
Surrogate Markers	5	Weeks 1-4 (pre-dose, 5, 24 and 48 hours) Week 6	85
	•	Total	267

6.7.6 Processing Blood Samples.

Blood sample each will be collected per **Table 11** above and Schedule of Events (**Table 12**) for Laboratory, Surrogate Marker measurements in a heparinized tube and immediately placed on ice. Within 30 minutes of collection, plasma will be isolated by centrifugation at $4^{\circ}C/1000*g$ for 10 minutes.

- CBC, Kidney function test, Liver Function test (7 mL): This is a test prior to dosing to demonstrate that the patient can safely be treated with methotrexate. The test will be performed at the laboratory used by the clinical site.
- Laboratory Test samples (14 mL): The plasma for the laboratory tests will be split into two equal parts, transferred into polypropylene freezer vials and then frozen at -20°C to -70°C. One of the two vials will be used for the Laboratory Tests performed at the site and the other vial will be sent to the central laboratory.
- Surrogate Marker samples (5mL). The plasma for sample) will be transferred to a polypropylene freezer vial and then frozen at -20°C to -70°C.

Specific shipping instructions will be issued by the analytical laboratory performing the analyses. The heparinized tube and freezer vial will be labeled with study code, subject number, subject initials, date and sampling time points. The plasma samples will be stored at the center until the study coordinator arranges transport to the analytical sites.

Laboratory test will be performed both at the central laboratory except . Assays used to measure surrogate markers will be performed at Tosk, or a CRO engaged by Tosk.

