8.2. SUBJECT WITHDRAWAL CRITERIA

A subject may voluntarily discontinue study participation at any time. At any time, the PI may also at his/her discretion discontinue a subject's study participation. Subjects may be withdrawn from this study for the following reasons:

- At the PI's discretion in situations where the subject is unable to comply, or complies poorly with the protocol.
- Disease progression and/or experiences intolerable toxicity.
- Major protocol violation.
- Lost to follow-up.
- If TK-112690/placebo treatment is delayed due to toxicity for more than 2 weeks.
- Inter-current event preventing administration of study medication for more than 2 weeks.
- Subject withdraws consent.
- Subject becomes pregnant.
- Subject starts any other chemotherapy agent or anti-cancer treatment other than study therapy for refractory solid tumor, e.g., radiation therapy.

• Death.

If there is an ongoing toxicity due to the study agent, subjects must be followed with appropriate medical management until resolution or stabilization, regardless of evidence of progressive disease.

The subject will be advised in the Informed Consent Forms that he/she has the right to withdraw from the study at any time without prejudice and may be withdrawn at the discretion of the PI or Tosk at any time. In the event that the subject drops out of the study or is withdrawn from the study, the withdrawal CRF should be completed. On the withdrawal page the PI should record the date of the withdrawal, the person who initiated withdrawal and the reason for withdrawal.

Reasonable effort should be made to contact any subject lost to follow-up during the course of the study in order to complete assessments and retrieve any outstanding data.

At the time of study withdrawal, following will be recorded for these premature removals:

- Update medical history including any additional cancer therapies, including starting date (immunotherapy, targeted therapy, radiation and surgical interventions) if known.
- Physical examination and determination of vital signs, weight and AEs.
- Laboratory tests (hematology, chemistry, coagulation and urinalysis).
- Mucositis assessment (Section 20.6, Appendix 6).

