10.2. POPULATIONS

10.2.1. Efficacy and Safety Population

The efficacy population will consist of all subjects who received at least four doses of TK-112690. The safety population will consist of all subjects who receive at least one dose of TK-112690.

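### Section 8.2 gives discretionary withdrawal to the blinded investigator in its operative text but also to the unblinded sponsor in its consent-form sentence, and no analysis rule protects the arm comparison from such a withdrawal

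*Combined protocol and SAP*

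**What the plan says.** **Who may withdraw a subject.** Section 8.2 opens by allowing the subject to leave at any time and the investigator to withdraw a subject at his or her discretion. A list of reasons follows, and none of them is a sponsor decision. Later, when describing what the consent form will tell the subject, the same section says that he or she "may be withdrawn at the discretion of the PI or Tosk at any time". No reason, reviewer or time limit is attached to the sponsor's part of that phrase.

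**Who knows the arm.** Section 3.5: "The CRO, sponsor, and site pharmacist will know whether the patient was administered active drug or placebo". Section 5.5 repeats this: "the CRO, Sponsor, and site pharmacist (unblinded) will know whether TK-112690 or placebo, was administered". The patient and the investigator are blinded.

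**What the sponsor receives.** Section 6.7.1, on central laboratory tests: "The laboratory will provide the PI and Tosk with test results including units, relevant reference ranges and updates as necessary". Section 6.7.4, on the blood count, kidney and liver tests before each methotrexate dose: "the data provided to the PI, the CRO and Tosk". Section 9.1.3 sends all serious adverse events to the sponsor. Under Section 11.6, sponsor or CRO monitors review collected data during the study.

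**Who is analysed.** Section 10.2.1: "The efficacy population will consist of all subjects who received at least four doses of TK-112690". No all-randomised population is defined. Section 10.4 covers only subjects lost to follow-up. Section 10.1.2 replaces only patients who drop out before completing first dosing.

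**What is recorded.** The withdrawal form in Section 8.2 captures the date, "the person who initiated withdrawal and the reason for withdrawal", and a mucositis assessment is made at withdrawal. Section 10.3 summarises withdrawals by dose group, and Section 10.3.1 summarises withdrawals due to adverse events by treatment group.

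**The concern.** Randomisation protects the comparison only while removal from it does not depend on knowing the arm. The operative part of 8.2 meets that condition, because the investigator is blinded. The consent-form sentence adds a decision-maker who is not blinded and attaches no criteria. If the sponsor withdrew a patient, a reader of the report could not tell from the plan whether the arm had influenced the decision, and the plan does not say how that patient would be analysed.

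With 11 patients per arm, one such removal can move the arm difference noticeably. The study is exploratory, but Section 10.1.1 hopes that the difference may reach statistical significance and expects the data to power the next study. Bias here would carry into that planning estimate.

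**Working it through.** The plan states no figure on this point: Section 10.1.1 says that the sample size does not come from a calculation. The check is therefore a reading of the passages together, followed by an illustration of scale.

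**Step 1: timing.** Randomisation is on Day 0 (Section 7.1.2, Table 12). Any withdrawal during treatment is after randomisation.

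**Step 2: the two parts of 8.2.** The operative sentence and the list name the investigator. The consent-form sentence names the investigator or the sponsor. Nothing elsewhere in the document limits or explains the sponsor's role in withdrawing one subject.

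**Step 3: what an early withdrawal does.** Entry to the efficacy set needs four doses, and the meaning of a dose is not fixed.

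- If each infusion is a dose, there are two per week (Synopsis, Table 12). The fourth is the second infusion on Day 1 of Week 2, and only withdrawal before then excludes the patient.
- If a dose is a weekly treatment, as the usage in Section 1.5.2.11 suggests, the fourth falls in Week 4, and withdrawal at any earlier point excludes the patient.
- In either case, a patient withdrawn after qualifying stays in the set with later scores missing and no stated handling.
- Read literally, the definition counts only doses of TK-112690, so it does not say how a placebo patient qualifies.

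**Step 4: scale, for illustration only.** Assumptions: no true effect, independent normal scores with SD 1, higher score worse, 11 per arm, two-sided t-test at 0.05. The plan specifies no such test.

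*Bias.* The expected largest of 11 standard normal values is 1.586 and the second largest is 1.062. Because the 11 values have expected sum zero, the arm mean after removing the worst values shifts as follows:

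- one removed: 1.586 / 10 = 0.159 SD
- two removed: (1.586 + 1.062) / 9 = 0.294 SD
- one removed on an early score with correlation r to the final score: r × 0.159, so 0.5 × 0.159 = 0.079 SD

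*False favourable results (simulation, at least 100,000 null trials per row):*

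| Removed | Basis of removal | Bias (SD) | Favourable p<0.05 |
|---|---|---|---|
| none | – | 0 | 2.5% |
| 1 worst active | final score known | 0.16 | 6.1% |
| 2 worst active | final score known | 0.30 | 10.9% |
| 1 worst active | early score, r = 0.5 (assumed) | 0.08 | 3.9% |
| 1 worst active | early score, r = 0.3 (assumed) | 0.05 | 3.2% |
| 1 worst active and 1 best placebo | final score known | 0.32 | 13% |
| 2 worst active and 2 best placebo | final score known | 0.59 | 33% |

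The last two rows require perfect knowledge of final scores and opposite removals in both arms. They are worst-case bounds and not expectations.

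**The case against.** Several points on the other side are sound.

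- **The phrase describes consent-form content.** A reader might infer that the plan gives the sponsor an unrestricted right to remove patients. The text does not require that reading: the operative sentence is investigator-only, and no procedure for sponsor withdrawal is given. What stands is the mismatch. The patient would be told of a power that the rest of 8.2 neither grants nor limits.
- **The sponsor is not the only party with arm and data.** The CRO is also unblinded and receives the same pre-methotrexate results.
- **The data expressly sent to the sponsor are laboratory results and serious adverse events.** A reader might infer that the sponsor watches the efficacy endpoint by arm. No passage sends mucositis scores to it on a schedule, and Section 6.7.1 gives no timing for the central results. Scores could be seen through monitoring under Section 11.6, and a serious mucositis event would arrive as a serious adverse event. Those routes are possible and indirect.
- **Safeguards exist.** Withdrawals are summarised by group, initiator and reason are recorded, and an exit mucositis score is taken, so an imbalance would be partly visible. But the planned summary is not split by initiator, and no rule brings the exit score into the comparison.
- **The analysis is descriptive.** No planned test can be inflated, so the percentages above only show scale. The bias in the arm difference does not depend on a test.
- **The main analytic weakness is the dose-dependent efficacy set.** This is true, because exclusion by any initiator acts through it. The sponsor phrase adds a route that is not blinded.

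**Conclusion.** The point holds as an inconsistency with a consequence for the analysis. Section 8.2 needs reconciling, because one part leaves discretionary withdrawal with a blinded decision-maker and another extends it to an unblinded one. Since the efficacy set depends on doses received and no rule covers patients withdrawn by decision, such a withdrawal could remove a patient from the comparison or leave later scores missing.

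Under the assumptions shown, one removal of the worst active patient is worth about 0.16 SD and takes false favourable results from 2.5% to about 6%. If the choice rests on an early score correlated 0.5 with the final one, the figures are about 0.08 SD and 4%. The 13% and 33% figures should not be read as the likely effect.

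The documents do not support any inference that the sponsor intends to remove patients by arm, or that such removal would go unseen.

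**What to change.** 1. **Reconcile the two parts of Section 8.2 and the matching consent-form sentence.** A sponsor-initiated discretionary withdrawal of a single subject should be raised with a written reason, through a medical monitor who has not seen the assignment, and decided by someone blinded to arm. The monitor's blinding should be stated: Section 5.5 has the monitor ask an unblinded statistician for the code, while Section 3.5 describes the sponsor as a whole as unblinded. Safety withdrawals and the sponsor's right to stop a site or the study stay unchanged.
2. **Section 10.2.1:** analyse mucositis in all randomised and dosed patients by assigned arm, using every score collected, including the assessment at withdrawal.
3. **Section 10.3:** add initiator and reason to the withdrawal summary by group that is already planned.

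**Cost.** A few sentences in the protocol and consent form, and one extended table from fields already collected. The downside is that the sponsor loses unblinded discretionary removal of single patients.

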9.0. ASSESSMENT OF SAFETY

9.1. SPECIFICATION OF SAFETY PARAMETERS

9.1.1. Adverse Events

An adverse event (AE) is any untoward medical occurrence in a patient or clinical Investigational subject administered a pharmaceutical product and which does not necessarily have a causal relationship with this treatment. An AE can be any unfavorable and unintended sign (including an abnormal laboratory finding), symptom, or disease temporally associated with the use of an Investigational product, whether or not related to the Investigational product. Pre-existing conditions which worsen during a study are to be reported as adverse events.

All adverse events, regardless of causal relationship, encountered during the clinical study will be reported on the AE page of the CRF (please see section 9.3). Intensity of AEs will be graded using the National Cancer Institute Common Terminology Criteria for Adverse Events (CTCAE, version 4.0) and reported in detail as indicated on the CRF. If an adverse event occurs which is not contained in the NCI-CTCAE, the four-point scale (mild, moderate, severe, life-threatening) below will be used.

Mild	discomfort noticed but no disruption of normal daily activity
Moderate	discomfort sufficient to reduce or affect daily activity
Severe	severe discomfort, inability to work or perform normal daily activity
Life threatening	represents an immediate threat to life

9.1.2. Laboratory Test Abnormalities

Laboratory test results will be recorded on the laboratory results pages of the CRF. Laboratory test value abnormalities as such should not be reported on the AE page of the CRF as adverse events, unless there is an associated clinical condition for which the subject is given treatment or concomitant treatment is altered, study treatment is interrupted/delayed or the dose of study drug is modified, or the subject is permanently discontinued from the study drug because of the abnormal test value.

9.1.3. Serious Adverse Event

A serious adverse event (SAE) is any untoward medical occurrence that at any dose:

- Results in death.
- Is life-threatening (subject is at immediate risk of death from the event as it occurred).
- Requires subject hospitalization or prolongation of existing hospitalization.
- Results in persistent or significant disability/incapacity.
- Is a congenital anomaly/birth defect.
- Other medically important condition.

All of the above criteria apply to the case as a whole and should not be confused with the outcomes of individual reactions/events. More than one of the above criteria can be applicable to the one event.

Important medical events that may not be immediately life-threatening or result in death or hospitalization may be considered an SAE when, based upon appropriate medical judgment, they may jeopardize the subject or require medical or surgical intervention to prevent one of the outcomes listed in the definition above. Examples of such medical events include allergic bronchospasm requiring intensive treatment in an emergency room or at home, blood dyscrasias or convulsions that do not result in hospitalization, or development of drug dependency or drug abuse.

The definition and reporting requirements of the ICH Guideline for Clinical Safety Data management, Definitions and Standards for Expedited Reporting Topic E2 will be adhered to (see **Appendix 5**).

All SAEs, whether or not deemed drug-related or expected, must be reported to Tosk and to the trial clinical research associate (clinical monitor).

9.1.4. Follow-up of Adverse Events

All adverse events (and treatments for them) must be documented throughout the Study Treatment Phase starting after the administration of the first dose of study medication and for 28 days after the last intake of study medication, and followed up/medically managed until the event is either resolved or adequately explained, even after the subject has completed his/her study treatment. Unrelated, mild or moderate events must be followed for 28 days after the last study drug administration. Serious, life threatening or related events must be followed until resolution, the subject's death, the start of a new cancer therapy or the relationship is re-assessed.

